9.3.11 Hepatocellular toxicity

Elevation of aminotransferases (ALT and AST): Evaluation of subjects with elevated transaminases or bilirubin should be individualized and guided by the presence of specific risk factors such as liver

conditions (e.g. liver cirrhosis, liver metastases, thrombosis of portal or hepatic vein), concomitant hepatotoxic medication, alcohol consumption, and cancer-related causes. Specifically, pembrolizumab is a potential cause of immune-mediated hepatitis and reactivation or flare of HBV or HCV in affected patients is a possibility. **Please see Section 9.5.3 for evaluation and management of liver toxicity and specific dosing instructions for both cabozantinib and pembrolizumab.**

9.3.12 Infections and infestations

Infections and abscesses should be treated with appropriate local care and systemic therapy. Cabozantinib should be interrupted if there are open wounds until adequate healing has taken place. For minor or mildly symptomatic infections (e.g. urinary tract infection, cellulitis), cabozantinib may be continued at the discretion of the investigator if the drug is believed to be unrelated and is not expected to worsen the infection.

9.3.13 Blood and lymphatic system disorders

Hematological toxicities (e.g. neutropenia, thrombocytopenia) have been observed after administration of cabozantinib. Subjects with hematologic toxicities may require additional or more frequent laboratory tests according to institutional guidelines.

See Section 9.5.1 for guidance on dose modification of cabozantinib for hematologic toxicities. The use of colony-stimulating growth factors may be considered for significant neutropenia (e.g. grade 3 or higher) believed to be related to cabozantinib. Febrile neutropenia or evidence of infection associated with neutropenia must be assessed immediately and treated appropriately and in a timely manner according to institutional guidelines, with interruption of study treatment until resolution.

Supportive care for thrombocytopenia or anemia, such as transfusions, may be considered according to institutional guidelines. However, if there is a recurrent need for transfusions or grade 3 events, dose reduction of cabozantinib to the next lower dose is recommended.

9.3.14 Fatigue

Common causes of fatigue, such as anemia, deconditioning, emotional distress (depression and/or anxiety), poor nutrition, dehydration, sleep disturbance, and hypothyroidism should be ruled out and treated according to standard of care.

For clinically significant fatigue (e.g. grade 3) related to or exacerbated by cabozantinib, dose interruption and/or dose reduction is recommended.

9.3.15 Weight loss

Anorexia and weight loss should be managed according to local standard of care including nutritional support. Pharmacologic therapy may be considered for appetite enhancement when not prohibited if there is minimal drug interaction with cabozantinib (see Section 8.4).

For clinically significant weight loss or anorexia (e.g. grade 3) related to or exacerbated by cabozantinib, dose interruption and/or dose reduction is recommended.

9.3.16 QTc prolongation

The effect of orally administered cabozantinib 140 mg once daily on QTc interval was evaluated in a placebo-controlled study in subjects with medullary thyroid cancer. A mean increase in QTcF of 10-15 ms was observed at 4 weeks after initiating cabozantinib treatment. A concentration-QTc relationship could not be definitively established. Changes in cardiac wave form morphology or new rhythms were not observed. No cabozantinib-treated subjects in this study had a QTcF > 500 ms.

Review of the larger safety database (~5000 subjects exposed to cabozantinib in clinical trials and in post-marketing experience) confirmed the absence of safety concerns associated with QT prolongation. There were no events of torsades de pointes reported.

Concomitant treatment with strong CYP3A4 inhibitors, which may increase cabozantinib plasma concentrations, should be avoided.

An EKG should be obtained every 2 cycles on treatment. At any time on study, if there is an increase in QTcF to an absolute value > 500 ms, two additional EKGs must be performed with intervals not less than 5 min apart within 30 min after the initial EKG.

If the average QTcF from the three EKGs is > 500 ms, the following actions must be taken:

- Interrupt cabozantinib treatment.
- Hospitalize symptomatic subjects (e.g. palpitations, dizziness, syncope, orthostatic hypotension, ventricular arrhythmia on EKG) for a thorough cardiology evaluation and management.
- Consider cardiology consultation for asymptomatic subjects for evaluation and management.
- Check electrolytes, especially magnesium, potassium and calcium; correct abnormalities as clinically indicated.
- Check for concomitant medications that may have contributed to QT prolongation, and if possible, discontinue these medications (<http://www.qtdrugs.org>).

Subjects with QTc prolongation and symptoms must be monitored closely until the QTc elevation and symptoms have resolved. Cabozantinib treatment may be restarted at a reduced dose level if all of the following conditions are met:

- Symptoms are determined to be unrelated to the QT interval prolongation.
- The QTcF value > 500 ms is not confirmed.
- Cabozantinib treatment has been interrupted through a minimum of 1 week following the return of the QTcF to ≤ 500 ms.
- QT prolongation can be unequivocally associated with an event other than cabozantinib administration and is treatable/has been resolved.

Following reinitiation of study treatment, EKGs must be repeated weekly for 2 weeks, then every 2 weeks for 1 month, then according to the protocol-defined time points.

Cabozantinib treatment must be permanently discontinued if either of the following applies:

- Cardiac evaluation confirms that symptoms are the consequence of QT interval prolongation.
- Recurrence of QTcF prolongation after reinitiation of study treatment at a reduced dose.

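### Read literally, the second QTcF restart condition in Section 9.3.16 bars every restart after a mandated hold; exclusion 19 has a smaller trigger mismatch (both low severity)

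*Combined protocol and SAP*

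**What the plan says.** **On-study rule (Section 9.3.16).** One QTcF above 500 ms calls for two further EKGs within 30 minutes. Then: "If the average QTcF from the three EKGs is > 500 ms, the following actions must be taken". The first action is to interrupt cabozantinib.

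For restart: "Cabozantinib treatment may be restarted at a reduced dose level if all of the following conditions are met". The four conditions are:

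1. The symptoms are judged unrelated to the QT prolongation.
2. "The QTcF value > 500 ms is not confirmed".
3. "Cabozantinib treatment has been interrupted through a minimum of 1 week following the return of the QTcF" to 500 ms or less.
4. "QT prolongation can be unequivocally associated with an event other than cabozantinib administration", and that cause is treatable or has resolved.

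Monitoring after restart is specified: "Following reinitiation of study treatment, EKGs must be repeated weekly for 2 weeks, then every 2 weeks for 1 month". There are two grounds for permanent discontinuation: symptoms shown to result from the prolongation, and recurrence after restart at a reduced dose.

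**Entry rule (exclusion 19, synopsis and Section 5.2).** QTcF above 480 ms within 28 days before the first dose excludes. A note adds that a single reading above 500 ms is followed by two more EKGs, and the mean of the three decides eligibility.

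**The concern.** Condition 2 does not say what would confirm the value, or when. Elsewhere the protocol attaches a method or a time to a confirmation: a second blood pressure at least 5 minutes later (Section 9.3.5), a second urine protein/creatinine reading within 1 week (Table 9.3.9.1), and ALT above 20 × ULN confirmed within 1 week (Section 12.0). In Section 9.3.16 the only candidate is the three-EKG mean, and that is the trigger for the hold.

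At stake is whether a patient whose QTcF has recovered, for example after a corrected electrolyte disorder, may go back on cabozantinib. One investigator could apply the bullet literally and refuse. Another could look at the rest of the section and allow it. The written rule does not settle which is right.

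For exclusion 19, the decision limit and the repeat trigger are different numbers, so candidates just above the limit are treated less favourably than candidates well above it.

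**Working it through.** The plan gives no figure of its own here to reproduce. The first part is a comparison of rules and the second is simple arithmetic.

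**1. Condition 2 against the hold trigger.** Let M be the mean QTcF of the three EKGs.

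- Mandated hold: M > 500 ms.
- Condition 2, with confirmation taken as the three-EKG mean: not (M > 500 ms), that is, M ≤ 500 ms.

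These are exact opposites. For M = 501 or 520 ms the hold applies and condition 2 is false, whatever the QTcF does later. Since all four conditions are required, restart is never allowed after a mandated hold.

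**2. That result against the rest of Section 9.3.16.**

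- Condition 3 speaks of a return to 500 ms or less, so it presupposes a real excursion above it.
- Condition 4 assigns the prolongation to another cause, so it also treats the prolongation as real.
- The post-restart EKG schedule and the recurrence rule could never operate after a mandated hold.
- A confirmed value above 500 ms is not among the two grounds for permanent discontinuation.

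The literal result therefore conflicts with the section's evident purpose. The reading that fits is a check made at restart.

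**3. Whether condition 3 already supplies that check.** Condition 3 counts at least 1 week of interruption after QTcF comes back to 500 ms or less. It does not say that QTcF must still be at or below 500 ms when the drug is restarted. If QTcF falls to 500 ms and later rises to 501 ms while the drug is off, the wording of condition 3 can still be satisfied. Condition 4 does not close the gap, because it accepts a cause that is only treatable. A condition 2 read as a check at restart would block this patient, so under that reading it has work to do.

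**4. Exclusion 19.** Eligibility after averaging requires (first + second + third)/3 ≤ 480 ms, so the two repeats must average at most (1440 − first)/2.

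| First reading (ms) | Repeats must average at most (ms) | Fall needed (ms) | Repeat called for? |
|---|---|---|---|
| 481 | 479.5 | 1.5 | No |
| 490 | 475.0 | 15 | No |
| 500 | 470.0 | 30 | No |
| 501 | 469.5 | 31.5 | Yes |
| 510 | 465.0 | 45 | Yes |

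Illustration with assumed readings:

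- 505/465/465 ms gives 1435/3 = 478.3 ms: eligible.
- A first reading of 490 ms is excluded on that reading alone, although 490/465/465 would give 1420/3 = 473.3 ms.

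**The case against.** **Intent is recoverable from context.** Conditions 3 and 4 and the post-restart rules show that restart is meant to be possible, so a careful reader would not apply the literal sense. This stands as an account of intent. It does not repair the wording: the bullet is one of four mandatory conditions, and nothing tells the investigator to read it differently.

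**The bullet has other possible meanings.** It would make sense if the drug had been held voluntarily after one high reading with a three-EKG mean of 500 ms or less, or if it referred to an over-read of the tracings. The first is fair but lies outside a mandated hold. For the second, the section provides for cardiology evaluation or consultation but names no over-read.

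**A stronger reading is tempting.** A reader might infer that the bullet is either impossible to meet or redundant, and so can simply be struck out. The documents do not support that. Redundancy requires the return to 500 ms or less to be sustained until restart, and condition 3 does not say so. Deleting the bullet could loosen a cardiac safeguard.

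**The practical reach is small.** This stands. In the 140 mg study, "No cabozantinib-treated subjects in this study had a QTcF > 500 ms", and a review of about 5000 exposed subjects "confirmed the absence of safety concerns associated with QT prolongation". Sections 9.2 and 9.5 let the investigator depart from the guidance. Section 9.3 sends resumption after more than 4 weeks to the PI and lets pembrolizumab continue. The literal reading also errs toward keeping the drug off.

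**Exclusion 19 is clear, and moving the trigger eases entry.** The limit is indeed clear, a repeat within the 28-day window is not forbidden, and Section 5.3 allows re-screening for a reversible cause. Some candidates at 481–500 ms would become eligible. They would still have to meet the same 480 ms limit on the mean that already applies to those with higher first readings.

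**Conclusion.** Both points hold at low severity.

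Condition 2 is wrong as written. Taken with the only repeat-EKG step described before the restart list, it forbids every restart after a mandated hold, against the plain purpose of the section. This rests on taking that three-EKG mean as the confirmation, because no other is named. The hold, the work-up and the permanent-stop rules work as they stand.

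The exclusion 19 mismatch is minor. It affects only candidates whose first reading is 481–500 ms, and the documents give no count of them. The table shows the fall that each first reading needs, not how likely that fall is, because the documents give no data on EKG variability.

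The documents give no rate of QTcF above 500 ms at 40 mg, so no frequency is estimated. A reader might infer lost treatment on a scale that matters for the response rate. Nothing in the documents supports that, and no effect on the primary analysis is claimed.

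**What to change.** **Section 9.3.16.** Keep a second restart condition but replace its wording with: *Repeat EKGs immediately before restart show QTcF of 500 ms or less*. Leave the other three conditions, the reduced dose, the post-restart EKG schedule and the permanent-stop rules unchanged. This removes the contradiction and adds the check at restart that condition 3 does not fully provide. The cost is one amended bullet and the repeat EKGs before a restart.

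**Exclusion 19, in both the synopsis and Section 5.2.** Change the repeat-and-average trigger from above 500 ms to above 480 ms. The 480 ms limit on the mean stays. The cost is one number changed in two places and two extra EKGs for each candidate whose first reading is 481–500 ms.

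Neither change affects the sample size or the analysis, and both can go into the next amendment.

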9.3.17 Electrolyte disorders

Serum electrolyte disorders including hyponatremia, hypokalemia, hypomagnesemia, and hypophosphatemia have been reported during treatment with cabozantinib, and serum electrolyte levels should be monitored at least every 3 weeks while receiving cabozantinib. More frequent monitoring may be required. Standard clinical practice guidelines should be used for management of electrolyte disorders and may include oral or intravenous replacement.

9.3.18 Angioedema

Angioedema should be managed according to standard practice. The subject should be observed until symptoms resolve, with particular attention to effects on airway. If life-threatening angioedema is probably or definitely related to cabozantinib, the drug must be discontinued.

9.3.19 Endocrine disorders

Treatment-emergent elevation of thyroid-stimulating hormone (TSH) has been observed with cabozantinib monotherapy treatment. Currently available data are insufficient to determine the mechanism of thyroid function test alterations and its clinical relevance.

TSH elevation may also be related to immune-mediated endocrinopathy caused by pembrolizumab, which occurs in 8% and 5% of patients in the KEYNOTE-224 and KEYNOTE-240 trials, respectively (mostly grade 1-2).^{35,36} TSH and free T4 and T3 should be checked at least every 6 weeks (every 2 cycles) on study.

Regardless of whether it is related to cabozantinib and/or pembrolizumab, clinically symptomatic hypothyroidism should be treated with thyroxine replacement as per accepted clinical practice guidelines. See Section 9.5.5 for treatment guidelines for suspected immune-mediated endocrine AEs.

9.4 Dose levels of cabozantinib

Cabozantinib must be started at 40 mg orally once daily and reduced to 20 mg orally once daily (minimum dose) for toxicity. Cabozantinib must be discontinued permanently if the minimal dose is not tolerated. Re-escalation to 40 mg once daily is not recommended, but may be allowed if there is a reason to believe that the patient will tolerate this dose after discussion with the PI.

Table 9.4.1. Dose levels for cabozantinib		
Dose Adjustment Level	Oral Dose	Frequency
0 (starting dose)	40 mg	Once daily
-1	20 mg	Once daily
-2		Discontinue

9.5 Guidance on dose modification of cabozantinib and pembrolizumab for non-immune and immune toxicities

Both non-immune and immune-mediated toxicities may occur on study.

The sections below provide guidance on dose modifications for TRAEs, in addition to management recommendations for cabozantinib-specific toxicities discussed in Section 9.3. However, management

RG1007034

may differ from this guidance based on the clinical judgement of the investigator. In all patients, supportive care should be initiated to manage the AEs in addition to dose modification of study drugs.

For potential irAEs, please refer to the ASCO Clinical Practice Guidelines for Management of Immune-Related Adverse Events in Patients Treated With Immune Checkpoint Inhibitor Therapy.⁵⁸

If dose is interrupted for TRAEs, cabozantinib must be resumed within 4 weeks of last dose, and pembrolizumab must be resumed within 12 weeks of last dose. Resuming drugs beyond these time points must be discussed with the Study PI.

9.5.1 Non-immune toxicities

Table 9.5.1.1 below provides guidance for dose modification for non-immune toxicities in general. Pembrolizumab should be held if the AE is clinically severe and/or if pembrolizumab might delay recovery or worsen the AE.

Table 9.5.1.1. General guidance on dose modification for non-immune toxicities

Grade per CTCAE v5	Cabozantinib modification	Pembrolizumab modification
Hematologic TRAEs		
Grade 1 and 2	
No modification.	
No modification.
Grade 3 or 4 anemia, neutropenia, thrombocytopenia ¹	
Hold drug until recovery to grade 1, then restart at same dose level OR at reduced dose level (at the discretion of the investigator).1st and 2nd recurrence: hold drug until recovery to grade 1, then restart at reduced dose level (if not already reduced) or discontinue drug (if previously reduced dose).	
No modification.No modification. Consider holding drug if no improvement after holding cabozantinib.
Non-hematologic TRAEs		
Grade 1 or 2	
No modification (may be held for significantly symptomatic grade 2 toxicity). Supportive care as indicated.	
No modification.
Grade 3	
Hold drug until recovery to grade 1. If supportive care can be used and optimized to control symptoms, then restart at the same dose level. If grade 3 toxicity occurred on maximal supportive care then restart at reduced dose level.	
Hold drug until recovery to grade 1 (or pretreatment baseline), then restart drug.

	
 • 1st and 2nd recurrence despite optimal supportive care: hold drug until recovery to grade 1, then restart at reduced dose level (if not already reduced) or discontinue drug (if previously reduced dose). 	
Grade 4	
 • Hold drug and provide supportive care until recovery to grade 1, then restart at reduced dose level if the patient is deriving clinical benefit as determined by the treating investigator. • 1st recurrence: discontinued drug. 	
 • Hold drug until recovery to grade 1 (or pretreatment baseline), then restart drug.

TRAE, treatment-related adverse event.

¹Supportive transfusions and use of G-CSF recommended as per institutional guidelines.

Note: Continuation of study drugs in the setting of asymptomatic grade 3-4 elevations of amylase/lipase is permitted after discussion with the study PI.

9.5.2 Diarrhea

Diarrhea is a known toxicity of both cabozantinib and immune checkpoint inhibitors such as pembrolizumab. In the CELESTIAL trial of cabozantinib (starting dose of 60 mg daily) vs. placebo, 54% of patients treated with cabozantinib had diarrhea of any grade, and 10% had grade 3 diarrhea. The median time of onset of diarrhea was 4.1 weeks.²¹ In the KEYNOTE-224 trial of pembrolizumab, 11% of patients experienced diarrhea (all grade 1-2, no grade 3 or 4), while the rate of immune-mediated colitis was 1%.³⁵ In the randomized KEYNOTE-240 trial, diarrhea occurred in 16% of patients on the pembrolizumab arm (1.2% grade 3-4).³⁶

The combination of multikinase inhibitor and immune checkpoint inhibitor may potentially increase diarrhea. However, the rate of diarrhea was similar with the combination of lenvatinib and pembrolizumab as observed in the early Phase 1b trial (any grade, 43%; grade 3, 3%) compared to lenvatinib alone (any grade, 39%; grade 3, 4%).^{10,38}

Enrolled patients should be closely monitored for diarrhea, and if present, attribution to cabozantinib or pembrolizumab or both must be carefully considered. Timing may guide attribution, as the onset of diarrhea related to cabozantinib tends to occur shortly after starting drug (e.g. within 2 weeks), while the median time to onset of immune-related colitis related to pembrolizumab was 3.5 months with a median duration of 1.4 months.

Recurrent or prolonged diarrhea can be associated with anal or perianal skin erosions, which increase the risk for anal abscesses, fistulas, or proctitis. Good personal hygiene should be emphasized. Examination of the perianal region should be performed for reported perianal symptoms in patients experiencing diarrhea during treatment with cabozantinib/pembrolizumab. Infections of the perianal region should be treated per local guidelines.

General management for diarrhea:

- Monitor patients for signs and symptoms of colitis (e.g. diarrhea, abdominal pain, bloody stools, fever) and bowel perforation. Administration of antidiarrheal/antimotility agents is recommended at the first sign of diarrhea as initial management (e.g. loperamide 4 mg followed by 2 mg after each episode of diarrhea [maximum: 16 mg loperamide per day]). Some subjects may require treatment with more than one antidiarrheal agent, and the addition of diphenoxylate/atropine and/or tincture of opium can be considered. In addition, general supportive measures should be implemented, such as increasing oral hydration (+/- IV isotonic fluids), correcting electrolyte abnormalities, small frequent meals, and stopping lactose-containing products, high-fat meals and alcohol. When diarrhea resolves to baseline bowel habits, gradually add solid foods and discontinue or decrease antidiarrheal treatment after 12 h diarrhea-free interval.
- For grade 1 and 2 diarrhea: supportive measures as above.
- For intolerable grade 2 diarrhea or grade 2 diarrhea >48 hours despite optimal supportive measures as above:
 - Obtain labs to rule out dehydration and electrolyte abnormalities.
 - Rule out infectious diarrhea (e.g. stool culture, C difficile toxin, enteric panel).
 - If diarrhea lasts > 7 days, consider imaging (e.g. CT abdomen/pelvis) and GI consult for colonoscopy for biopsy.
- If infectious source is ruled out and diarrhea is persistent > 7 days, suspect immune-mediated colitisFor severe and/or life-threatening diarrhea:
 - Admit to hospital for IV hydration and electrolyte replacements.
 - Rule out infectious diarrhea (e.g. stool culture, C difficile toxin, enteric panel).
 - Obtain imaging (e.g. CT abdomen/pelvis) and GI consult for colonoscopy for biopsy.
 -
- See Table 9.5.2.1 for dosing of cabozantinib and pembrolizumab in the setting of non-immune diarrhea. For suspected immune-mediated colitis, also follow guidelines in Table 9.5.5.1.

Table 9.5.2.1. Guidance for diarrhea due to cabozantinib (non-immune)

Grade per CTCAE v5	Cabozantinib modification	Pembrolizumab modification
Grade 1 (< 4 stools/day over baseline)	
 • Continue at same dose. 	
 • Continue at same dose.
Grade 2 (4-6 stools/day over baseline)	
 • Continue at same dose, or if intolerable grade 2 or grade 2 >48 hours despite optimal supportive measures and anti-diarrheals, hold drug until improvement to grade 1, then restart at same dose or at reduced dose (at the discretion of the investigator). 	
 • Continue at same dose.

Grade 3 (7 or more stools/day over baseline)	
 Hold drug until recovery to grade 1, then restart at same dose (if best supportive care was not previously used) or at reduced dose (if diarrhea is uncontrolled despite best supportive care). 1st recurrence: hold drug until recovery to grade 1, then restart at reduced dose (if not already done) or discontinue drug (if dose previously reduced). 	
 Hold drug until recovery to grade 1 (or pretreatment baseline), then restart drug.
Grade 4 (life-threatening)	
 Hold drug until recovery to grade 1, then restart at reduced dose level if the patient is deriving clinical benefit as determined by the treating investigator. 1st recurrence: discontinue drug. 	
 Hold drug until recovery to grade 1 (or pretreatment baseline), then restart drug.

